 Participants will receive Aggrenox (Dipyridamole ER 200mg/ Aspirin 25mg orally/enterally), 2 times daily (FDA–recommended dose) starting on the day of enrollment for a total of 2 weeks + standard care.
- Standard care Comparator: Participants will receive standard care starting on the day of enrollment for a total of 2 weeks.

2. Subject Enrollment

- 1. Patients who are eligible for the study will be enrolled in the clinical trial after they or their authorized proxy provide informed consent for study participation. A copy of the institution's IRB approved informed consent will be on file RedCap. The patients will be enrolled through RedCap, the Clinical Trials Management System for this study. Contact the Rutgers Clinical Trials Unit, if you have any questions about the Registration/Enrollment process.
- Registration: Any subject that has signed the consent will be entered into RedCap. A Copy of the consent will be uploaded into the Documents section.
- Enrollment: Once eligibility has been confirmed, the completed, signed and dated eligibility checklist will be uploaded into the Documents section. RedCap will randomize the patient and a sequence number (subject study ID) will be generated at the time of enrollment, this is the point the patient is considered on study.

Protocol Title: ATTAC-19 – Aggrenox To Treat Acute Covid-19 Pro#2020001469

Rutgers, The State University of New Jersey [name]

Patients will not start protocol treatment prior to registration.

3. Study Safety Assessments

The Principal Investigator is responsible for ensuring that all staff involved in the study are familiar with the content of this section.

Definitions:

Adverse Events:

An adverse event is the development of an undesirable medical condition or the deterioration of a pre-existing medical condition following or during exposure to a pharmaceutical product, whether considered causally related to the product. An undesirable medical condition can be symptoms (e.g. nausea, chest pain), signs (e.g. tachycardia, enlarged liver) or the abnormal results of an investigation (e.g. laboratory findings, electrocardiogram). In clinical studies, an AE can include an undesirable medical condition occurring at any time, including run-in or washout periods, even if no study treatment has been administered. The term AE is used to include both serious and non- serious AEs.

Serious Adverse Events:

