A serious adverse event is an AE occurring during any study phase (i.e., screening, run- in, treatment, wash-out, follow-up), at any dose of the study drugs that fulfills one or more of the following criteria and deemed secondary to the use of study drug:

- Results in death
- Is immediately life-threatening
- > Requires in-patient hospitalization or prolongation of existing hospitalization
- Results in persistent or significant disability or incapacity
- > Is a congenital abnormality or birth defect
- Is an important medical event that may jeopardize the patient or may require medical intervention to prevent one of the outcomes listed above.
- 1.1.1 The causality of SAEs (their relationship to all study treatment/procedures) will be assessed by the investigator(s) and communicated to Boehringer Ingelheim (BI) via BI SAE form and the FDA via MedWatch form, if applicable.

Causality will be reported as either "Yes" or "No".

- Yes: There is a reasonable causal relationship between the investigational product administered and the AE.
- ➤ No: There is no reasonable causal relationship between the investigational product administered and the AE.

2. Recording of Adverse Events

Rutgers, The State University of New Jersey [name]

Non-serious adverse events and SAEs will be determined from the time the patient is enrolled into the study and up to and including the 2 weeks follow-up period (after the completion of 2 weeks of treatment with Aggrenox) for a total of 28 days . All grade 3 or higher AEs will be recorded. Grade 1-2 AEs do not need to be recorded. After withdrawal from treatment, subjects must be followed-up for all existing and new AEs for 14 calendar days after the last dose of trial drug and/or until event resolution. All new AEs occurring during that period must be recorded (if SAEs, they must be reported to the DSMB and Rutgers IRB as per SOPs.). AEs will be recorded per Rutgers IRB SOPs. The common terminology criteria for adverse events (CTCAE) will be used as a reference to grade the adverse events.

(https://ctep.cancer.gov/protocoldevelopment/electronic_applications/docs/CTCAE_v5_Quick_R eference_8.5x11.pdf (Accessed on March 09, 2018)

All study-related adverse events/ SAEs must be followed until resolution, unless in the Treating Investigator's opinion, the condition is unlikely to resolve due to the patient's underlying disease.

3. Reporting of Serious Adverse Events

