Investigators and other site personnel must inform the Rutgers IRB per the SOPs on the required forms. FDA will be informed per SOP, via a MedWatch, of any serious or unexpected adverse events that occur in accordance with the reporting obligations of 21 CFR 312.32. It is the responsibility of the principal investigator to compile all necessary information and ensure that the FDA receives a report according to the FDA reporting requirement timelines.

In addition to FDA, the Sponsor shall report all SAEs and non-serious AEs that occur ,throughout the treatment period and up to and including the 2 weeks follow-up period (after the completion of 2 weeks of treatment with Aggrenox) for a total of 28 days which are relevant for a reported SAEs and any AEs relevant to a reported SAE by fax or other secure method using BI IIS SAE form to the BI Unique Entry Point in accordance with timeline specified in the safety data exchange agreement .

For each adverse event, the investigator will provide the onset date, end date, causality, intensity, treatment required, outcome, seriousness, and action taken with the investigational drug.

The investigator does not need to actively monitor patients for adverse events once the clinical trial has ended. However, if the investigator becomes aware of an SAE(s) that occurred after the patient has completed the clinical trial (including any protocol specified follow-up period), it should be reported to BI if investigator considers it as relevant to the BI study drug.

All SAEs meeting the criteria for expedited reporting will be reported to the Rutgers IRB within the mandated time frames. All SAEs within the safety follow-up window (e.g., within 14 days after the last dose of study medications) established in the protocol will be reported.

Non-serious adverse events and SAEs will be collected from the time the patient is enrolled into the study, throughout the treatment period and up to and including the 2 weeks follow-up period (after the completion of 2 weeks of treatment with Aggrenox) for a total of 28 days. After withdrawal from treatment, subjects must be followed-up for all existing and new AEs for 14 calendar days after the last dose of trial drug and/or until event resolution. All new AEs

Protocol Title: ATTAC-19 – Aggrenox To Treat Acute Covid-19 Pro#2020001469

Rutgers, The State University of New Jersey [name]

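### The SAE definition requires attribution to study drug, which contradicts the separate causality assessment of SAEs and, read literally, leaves the standard-care arm unable to have an SAE

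*Combined protocol and SAP*

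**What the plan says.** All of the relevant text is in the combined protocol, mostly in section 1.2 Research Design and Methods.

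- **Definition (Serious Adverse Events).** The sentence opens "A serious adverse event is an AE occurring during any study phase (i.e., screening, run- in, treatment, wash-out, follow-up" and goes on to limit SAEs to events "that fulfills one or more of the following criteria and deemed secondary to the use of study drug". Two conditions must therefore both hold: a seriousness criterion and attribution to the drug.
- **Causality (the item that follows).** "The causality of SAEs (their relationship to all study treatment/procedures) will be assessed by the investigator(s"), with a Yes or No answer. No is defined as: "No: There is no reasonable causal relationship between the investigational product administered and the AE".
- **Fields per event (Reporting of Serious Adverse Events).** Causality and seriousness are listed as separate items for every adverse event.
- **Routes tied to the label (same heading).** To the IRB: "All SAEs meeting the criteria for expedited reporting will be reported to the Rutgers IRB within the mandated time frames". To the manufacturer: "the Sponsor shall report all SAEs and non-serious AEs that occur", within the 28-day period. Under Recording of Adverse Events and again under Clinical Safety Assessments, new events after withdrawal from treatment go to the DSMB and IRB if they are SAEs.
- **Collection window.** Recording of Adverse Events and Reporting of Serious Adverse Events start collection at enrolment and run to 28 days. Clinical Safety Assessments starts it when study drug is given.
- **Design.** Open-label, 1:1, 66 patients per arm (sections 1.1 and 1.2). The control arm receives standard care alone.

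No other part of the protocol defines an SAE, and none gives a definition for the standard-care arm.

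**The concern.** Seriousness (what happened to the patient) and causality (whether the drug did it) are normally two judgements. Here the first contains the second, and the text then asks for the second again as though it were still open. Staff can follow the definition, or follow the causality item, but not both, and the protocol does not say which governs.

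The trial is open-label, so whoever makes the attribution knows the allocation. If the definition is followed, that judgement decides which serious events are called SAEs and enter the manufacturer and IRB reports, and the DSMB and IRB reports of new events after withdrawal. The protocol's own content makes disputed attribution foreseeable: section 4.7 says Aggrenox raises bleeding risk and names heparin as a further risk factor, while section 4.1 admits patients on prophylactic heparin or enoxaparin. A serious bleed attributed to heparin alone would not be an SAE in the Aggrenox arm, and the same bleed in a standard-care patient could never be one.

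**Working it through.** The protocol states no figure on this point, so there is none to reproduce. The check is one of logic, with one count.

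**1. Definition against causality item.** Let S mean that a seriousness criterion is met and D mean that the event is deemed secondary to study drug.

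- Definition: SAE = S and D.
- Causality item: among SAEs, answer Yes (D) or No (not D).
- SAEs answered No = S and D and not D, which is empty.

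So No can never be entered for an SAE, although the protocol provides it for exactly that assessment. The item also extends to study procedures; an SAE due to a procedure alone is likewise impossible under the definition. No remains usable for other adverse events, but the item is worded for SAEs.

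**2. Definition against its own phase list.** Screening is a named phase. In the Day 0 list under Study Procedures, randomisation is the last step, so no study drug can have been given before it. A screening event cannot satisfy D. This is a secondary sign of the same problem: naming the phase has no effect.

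**3. Definition against the fields per event.** Separate entries for causality and seriousness fit a definition SAE = S. They do not strictly contradict SAE = S and D, but they show that the two judgements were meant to be recorded apart.

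**4. Consequence by arm, on the literal reading.** Inputs: 132 patients, 66 per arm (section 1.1); no study drug in the control arm (section 1.2).

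- Standard care: D is false for every event, so patients with an SAE = 0 of 66, whatever happens. Share of the trial affected = 66/132 = 0.50.
- Aggrenox: with A serious events and a fraction f attributed to the drug, SAEs = f × A. Neither is given in the documents. Bounds: f = 0 gives 0; f = 1 gives A.

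**5. Consequence on the other reading.** If staff treat every event meeting S as an SAE and then answer Yes or No, no label is lost in either arm.

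**6. What is recorded regardless of D.** All grade 3 or higher adverse events; all-cause mortality at days 15 and 28; thromboembolic complications at day 28. The adverse-event outcome in section 1.6 is number, percentage and grade, which does not use the SAE label.

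**The case against.** **The Yes/No step may simply document the attribution.** Its two answers are defined in terms of an adverse event, so it could be how the second condition is decided. This is the best reconciliation, but it is incomplete: the item speaks of events already called SAEs, widens the question to procedures, and permits No.

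**The phase list is template text.** It also names run-in and wash-out, which this design does not have. A phase that yields no events is redundant rather than contradictory. That is fair, and the point is secondary here. The statement "Patients will not start protocol treatment prior to registration" does not settle it either, since registration follows consent and comes before eligibility is confirmed; only the order of the Day 0 steps does.

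**The 50% is a tautology.** It restates that controls receive no drug. Correct: it follows from the wording and does not estimate missed events.

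**Stronger readings that a reader might infer, and that the documents do not support:**

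- *That the protocol elsewhere presupposes drug-unrelated SAEs.* For events after trial completion it says "it should be reported to BI if investigator considers it as relevant to the BI study drug". But section 1.1 allows brand or generic drug, so an event could be due to study drug without concerning the manufacturer's product, and such events lie outside the trial phases in the definition.
- *That control-arm safety data are lost.* They are not; step 6 of the working lists what is recorded in any case. The seriousness field also helps, though only partly, because staff may complete it using the same definition.
- *That FDA reporting is cut off.* That route is worded more broadly, covering serious or unexpected events.
- *That the DSMB would be blind to SAEs generally.* Section 6.3 lists SAEs among the matters monitored but sets no reporting rule, so only the post-withdrawal route can be cited.
- *That an SAE comparison between arms is biased.* None is planned.

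**Deleting the clause has a cost.** All patients are inpatients, and prolonged hospitalisation and death are both seriousness outcomes and reflected in the primary scale. This stands and is taken up in the fix.

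**Conclusion.** The definition and the causality item cannot both be followed, and this should be corrected. Confidence is high on the wording conflict and lower on its practical effect.

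On the literal reading, 66 of 132 randomised patients cannot have an SAE, and the Aggrenox count ranges from none to all of its serious events, depending on an unblinded attribution. On the other reading nothing is lost. The protocol does not say which applies, gives no serious-event or attribution rate, and refers to IRB SOPs and a safety data exchange agreement that are not in the documents. The extent to which actual reports would be filtered is therefore unknown, and no narrower figure is offered.

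What is at risk is the SAE label and the manufacturer, IRB and post-withdrawal DSMB reports that depend on it. The underlying events, the endpoints and every planned analysis are unaffected.

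**What to change.** 1. In the SAE definition, delete the attribution clause (the second condition in the quoted sentence), so that seriousness is judged the same way in both arms.
2. Keep causality as the existing separate Yes/No assessment, and leave the expedited-reporting criteria as they are.
3. Reconcile the start of collection in Clinical Safety Assessments, which is tied to giving study drug, with the enrolment-to-28-days window in the recording and reporting sections. A standard-care patient has no first dose. The requirement that all evaluations be done in every randomised patient already points to the enrolment-based window.
4. State how deaths, prolonged hospitalisations and other events that are also reflected in the primary ordinal scale are handled in SAE reporting.

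The cost is a wording amendment and more SAE forms in both arms, possibly many more among inpatients with COVID-19; item 4 is there to manage that load. Sample size, endpoints and analyses do not change.

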Change (as compared to baseline on day 0) in composite COVID ordinal scale at day 15 Ordinal scale: 1) not hospitalized with resumption of normal activities; 2) not hospitalized, but unable to resume normal activities; 3) hospitalized, not requiring oxygen; 4) hospitalized, requiring oxygen; 5) hospitalized, requiring high-flow oxygen therapy, or noninvasive ventilation; 6) hospitalized, requiring invasive ventilation; 7) ventilation plus additional organ support such as vasopressors, renal replacement therapy and ECMO and 8) death.

Secondary endpoints:

- 1) all-cause mortality assessed on day 15 and day 28.
- 2) oxygen-free days through day 28.
- 3) invasive-ventilator-free days through day 28.

Protocol Title: ATTAC-19 – Aggrenox To Treat Acute Covid-19 Pro#2020001469

Rutgers, The State University of New Jersey [name]

- 4) ICU-free days through day 28.
- 5) hospital-free days through day 28.
- 6) increase in cycle threshold (Ct) of SARS-CoV-2 PCR test as an approximation of decline in viral load at days 7 and 15.
- 7) Change in the inflammatory markers D-dimer/ ferritin/ c-reactive protein at days 7 and 15 as compared to baseline on day 0.
- 8) thromboembolic complications including stroke at day 28.
- 9) Change (as compared to baseline on day 0) in COVID ordinal scale at day 28.
- 10) if feasible urine will be analysed for markers of tubular injury IL-18, kidney injury molecule-1 [KIM-1], neutrophil gelatinase-associated lipocalin [NGAL]), inflammation (monocyte chemoattractant protein-1 [MCP-1]), and repair (human cartilage glycoprotein-40 [YKL-40]

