1.6 Study Variables

A. Independent Variables, Interventions, or Predictor Variables

The following variables will be examined for treatment outcomes of efficacy and/or predict outcomes:

- Treatment
- Baseline temperature
- Baseline SARS-CoV test
- Baseline measure of inflammatory markers

B. Dependent Variables or Outcome Measures

The following variables will be examined for changed as result of treatment or as predictors

- Treatment Compliance
- Change in the fever curve
- Improvement in vital signs
- Time to discharge (if hospitalized)
- Adverse Events (number/percentage/grade)
- Inpatient versus Outpatient
- Change from baseline SARS-CoV test
- Change from baseline inflammatory markers

RUTGERS | eIRB APPROVED

Approval Date:

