- 4. Lab test result pending plus a high clinical suspicion for SARS-CoV-2 (fever and cough for ≤ 7 days, bilateral pulmonary infiltrates on imaging or new hypoxemia with spO2 ≤94% on room air or no alternative explanation for respiratory symptoms).
- 5. Willing and able to provide consent or by authorized proxy.

Exclusion Criteria:

- 1. Pregnancy.
- 2. History of G-6PD deficiency.
- 3. Use of antiplatelet agents including inhibitor of P2Y12 ADP platelet receptors, phosphodiesterase inhibitors, and Glycoprotein IIB/IIIA inhibitors.
- 4. On therapeutic anticoagulation with coumadin, unfractionated heparin, enoxaparin (lovenox) and direct oral anticoagulants. (prophylactic anticoagulation is now standard of care and patients on prophylactic anticoagulation such as enoxaparin or unfractionated heparin, will be included in the study)
- 5. Vasodilatory shock.
- 6. Patient with known ongoing angina, recent myocardial infarction and sub-valvular aortic stenosis.
- 7. Active gastric or duodenal ulcer or any bleeding disorder or creatinine clearance < 10.
- 8. Hemoglobin <9 mg/dL, platelet count of <30,000 /mm³.
- 9. Acute respiratory infection for >10 days.
- 10. Known allergy/hypersensitivity to Dipyridamole and/or Aspirin.
- 11. Severe hepatic or renal insufficiency.
- 12. Uncontrolled hypertension defined as systolic > 180 mm Hg or diastolic > 100 mm Hg.
- 13. Patients with known allergy to NSAIDs
- 14. Patients enrolled in other non-standard of care clinical trials.

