4.7 Risks of Harm/Potential for Benefits to Subjects

A. Description of Risks of Harm to Subjects

Reasonably Foreseeable Risks of Harm (this data I got from Aggrenox product information available online- Appendix is attached for your review))

Risk of Bleeding

AGGRENOX increases the risk of bleeding.

Risk factors for bleeding include the use of other drugs that increase the risk of bleeding (e.g., anticoagulants, antiplatelet agents, heparin, anagrelide, fibrinolytic therapy, and chronic use of NSAIDs).

Intracranial Hemorrhage In European Stroke Prevention Study-2 (ESPS2), the annualized event rate for intracranial hemorrhage was 0.39%/year in the AGGRENOX group, 0.26%/year in the extended-release dipyridamole (ER-DP) group, 0.24%/year in the aspirin (ASA) group, and 0.29%/year in the placebo groups.

Gastrointestinal (GI) Side Effects

GI side effects include stomach pain, heartburn, nausea, vomiting, and gross GI bleeding. Although minor upper GI symptoms, such as dyspepsia, are common and can occur anytime during therapy, physicians should remain alert for signs of ulceration and bleeding, even in the absence of previous GI symptoms. Inform patients about the signs and symptoms of GI side effects and what steps to take if they occur. In ESPS2, the annualized event rate for gastrointestinal bleeding was 2.97%/year in the AGGRENOX group, 1.58%/year in the extended-release dipyridamole group, 2.06%/year in the aspirin group, and 1.40%/year in the placebo groups.

Peptic Ulcer Disease

Avoid using aspirin in patients with a history of active peptic ulcer disease, which can cause gastric mucosal irritation and bleeding.

Alcohol Warning

Because AGGRENOX contains aspirin, counsel patients who consume three or more alcoholic drinks every day about the bleeding risks involved with chronic, heavy alcohol use while taking aspirin.

Renal Failure

Avoid aspirin in patients with severe renal failure (glomerular filtration rate less than 10 mL/minute) [see Use in Specific Populations.

Hepatic Insufficiency

Elevations of hepatic enzymes and hepatic failure have been reported in association with dipyridamole administration.

Coronary Artery Disease

Protocol Title: ATTAC-19 – Aggrenox To Treat Acute Covid-19

Pro#2020001469

Protocol Version 6 Date: 4/18/2021

7/21/2021

Rutgers, The State University of New Jersey [name]

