Patients taking AGGRENOX in combination with anticoagulants, antiplatelets, or any substance impacting coagulation are at increased risk for bleeding. Aspirin can displace warfarin from protein binding sites, leading to prolongation of both the prothrombin time and the bleeding time. Aspirin can increase the anticoagulant activity of heparin, increasing bleeding risk.

Anagrelide

Patients taking aspirin in combination with anagrelide are at an increased risk of bleeding.

Anticonvulsants

Salicylic acid can displace protein-bound phenytoin and valproic acid, leading to a decrease in the total concentration of phenytoin and an increase in serum valproic acid levels.

Protocol Title: ATTAC-19 – Aggrenox To Treat Acute Covid-19 Pro#2020001469

Protocol Version 6 Date: 4/18/2021

IRB ID: Pro202 Approval Date: Expiration Date:

Beta Blockers

The hypotensive effects of beta blockers may be diminished by the concomitant administration of aspirin due to inhibition of renal prostaglandins, leading to decreased renal blood flow and salt and fluid retention.

Cholinesterase Inhibitors

Dipyridamole may counteract the anticholinesterase effect of cholinesterase inhibitors, thereby potentially aggravating myasthenia gravis.

Diuretics

The effectiveness of diuretics in patients with underlying renal or cardiovascular disease may be diminished by the concomitant administration of aspirin due to inhibition of renal prostaglandins, leading to decreased renal blood flow and salt and fluid retention.

Methotrexate

Salicylate can inhibit renal clearance of methotrexate, leading to bone marrow toxicity, especially in the elderly or renal impaired.

Nonsteroidal Anti-Inflammatory Drugs (NSAIDs)

The concurrent use of aspirin with other NSAIDs may increase bleeding or lead to decreased renal function.

Oral Hypoglycemics

Moderate doses of aspirin may increase the effectiveness of oral hypoglycemic drugs, leading to hypoglycemia.

Uricosuric Agents (probenecid and sulfinpyrazone)

Salicylates antagonize the uricosuric action of uricosuric agents.

ADVERSE REACTIONS (please see Appendix C for further details)

Clinical Trials Experience

Table.1 Incidence of Adverse Events in ESPS2a

Individual Treatment Group

Body System/Preferred Term:

	AGGRENOX	ER-DP Alone	ASA Alone n	Placebo n
	n (%/year) ^b	n (%/year) ^b	(%/year) ^b	(%/year) ^b
Total Number of Patients	1650	1654	1649	1649
Central and Peripheral				
Nervous System				
Disorders				

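### Grade 1-2 adverse events need not be recorded, with no exception for bleeding, so low-grade bleeding on Aggrenox plus prophylactic heparin will not be systematically captured, and the recording text differs between arms

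*Combined protocol and SAP*

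**What the plan says.** All references are to the combined protocol and SAP.

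- **The floor.** Section 1.2 (Research Design and Methods) has two subsections called Recording of Adverse Events, one under Study Safety Assessments and one under Clinical Safety Assessments. Both say "All grade 3 or higher AEs will be recorded. Grade 1-2 AEs do not need to be recorded". Neither makes an exception for bleeding or for events of special interest.
- **After withdrawal from treatment.** Both subsections add, for the 14 days following the last dose and/or until the event resolves, "All new AEs occurring during that period must be recorded (if SAEs, they must be reported to the DSMB and Rutgers IRB as per SOPs". No grade is stated there.
- **Start of recording.** The first of the two starts at enrollment and runs to 28 days in total. The second starts when study drug is given. Reporting of Serious Adverse Events, between them, says "Non-serious adverse events and SAEs will be collected from the time the patient is enrolled into the study".
- **The risk.** Section 4.7 opens its list of foreseeable risks with "AGGRENOX increases the risk of bleeding" and, under drug interactions, says "Aspirin can increase the anticoagulant activity of heparin, increasing bleeding risk".
- **The population.** Section 4.1 excludes therapeutic anticoagulation, but "patients on prophylactic anticoagulation such as enoxaparin or unfractionated heparin, will be included in the study", and it calls such prophylaxis standard of care.
- **The endpoints.** None of the ten secondary endpoints is bleeding. The eighth is "thromboembolic complications including stroke at day 28".

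**The concern.** The protocol names a harm, names a co-medication that increases it, expects that co-medication as standard care, and then sets a recording rule that lets the milder part of the harm go unrecorded. The possible thrombotic benefit has a listed endpoint; the matching bleeding cost has none.

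There is a second problem, separate from the grade. Parts of the text depend on a first or last dose of study drug. The control arm receives none. If staff follow the text literally, the arms are observed under different rules, and a by-arm table of adverse events would partly reflect the rules and not the treatment.

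**Working it through.** **1. Recording rules by arm** (all in Section 1.2, Research Design and Methods)

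| Text | Grades | Window | Can it apply to controls? |
|---|---|---|---|
| Recording of Adverse Events, under Study Safety Assessments | 3 and above | Enrollment to day 28 | Yes |
| Reporting of Serious Adverse Events, collection sentence | None stated | Enrollment to day 28 | Yes |
| Recording of Adverse Events, under Clinical Safety Assessments | 3 and above | Starts when study drug is given | No: no study drug |
| After-withdrawal sentence, in all three places | None stated | 14 days from last dose and/or until resolution | No: no last dose |

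Illustration: an Aggrenox patient stops on day 4. New events of every grade must be recorded to day 4 + 14 = 18. A grade 1 bleed on day 10 is therefore recorded for that patient. The same bleed on day 10 in a control patient need not be.

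**2. What else could pick up a bleed**

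- Serious adverse events: the definition requires the event to be attributed to study drug. A serious control-arm bleed would not meet it as written, although at grade 3 or above it would be recorded as an adverse event under the enrollment-based rule.
- Blood counts and coagulation results are abstracted from the record at days 7 and 14. They do not identify a low-grade bleed, and follow-up after discharge may be by phone.
- Concomitant medications are collected. They show heparin exposure, which allows tabulation by heparin use, but they do not show bleeding.

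**3. Size**

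The plan gives no figure for bleeding or for adverse-event precision. Its only relevant number is the denominator, 66 per arm (Section 1.5). That reproduces: with a difference of 0.2 × 4.5 = 0.9, SD 1.6, 90% power and two-sided 5%, n = 2 × (1.960 + 1.282)² × 1.6² / 0.9² = 66.4, or 67 per arm against 66 stated.

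The remaining inputs are assumptions: p, the 28-day risk of any-grade bleeding, and s, the share of bleeds at grade 3 or above. Expected patients with a bleed per arm are 66 × p if all grades are recorded and 66 × p × s under the floor. The share lost is 1 − s, whatever p is.

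| Assumed p | All grades, 66 × p | Floor, s = 25% |
|---|---|---|
| 2% | 1.3 | 0.3 |
| 5% | 3.3 | 0.8 |
| 10% | 6.6 | 1.7 |
| 20% | 13.2 | 3.3 |

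- For s from 10% to 50%, the floor loses 90% to 50% of bleeds.
- At p = 10%, the chance that an arm shows no recorded bleed under the floor is (1 − 0.10 × s)^66 = 0.52, 0.19 and 0.03 for s = 10%, 25% and 50%. With all grades recorded it is 0.90^66 = 0.001.
- Power at 66 per arm (normal approximation, two-sided 5%) to detect a doubling from 10% to 20% is about 36% with all grades. With s = 25% under the floor, the contrast is 2.5% against 5% and power is about 11%.

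Recording all grades therefore improves description. It does not turn bleeding into something this trial can test.

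**The case against.** The strongest defense is that this is a small pilot of a marketed product and a grade floor is an ordinary economy. Section 4.1 already excludes therapeutic anticoagulation, other antiplatelet agents, active ulcer, bleeding disorders, low hemoglobin and low platelets. Minor bleeding is also prone to differential reporting in an open-label trial. The case report form modules (Appendix B) and the institutional SOPs are not in the text provided, so a bleeding item there cannot be ruled out. All of this stands, and it limits what the extra data can show. It does not cure a stated rule without a bleeding exception, or text that cannot be applied to controls.

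Four stronger readings are tempting and are not supported.

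- *The trial cannot describe bleeding on heparin at all.* It can: grade 3 or higher bleeding is recorded and can be tabulated by heparin use.
- *Low-grade events are barred, so those that lead to stopping the drug are invisible.* The text says they need not be recorded. After withdrawal, existing events are followed and new ones recorded, and each recorded event carries the action taken with the drug. What is missing is an explicit rule for the event that caused the stop.
- *Every adverse-event sentence conflicts with the floor.* Non-serious does not mean grade 1-2, since a grade 3 event can be non-serious. Listing grade as an outcome in Section 1.6 is satisfied by grades 3 and above. The real inconsistencies are the after-withdrawal sentence and the two start points.
- *The stroke-prevention rates in Section 4.7 measure the loss.* At 2.97% per year for gastrointestinal bleeding, 14 days on drug give 66 × 14/365.25 = 2.53 patient-years and 0.075 expected events. That reflects short exposure and a small sample. No grade is given for the rate, and the population was a chronic one. Likewise, the exact two-sided upper limit for 0 events in 66, 1 − 0.025^(1/66) = 5.4%, is the same with or without a floor. The long-term discontinuation percentages there do not describe a two-week course.

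**Conclusion.** The point holds in a limited form. Followed as written, the plan captures grade 3 or higher bleeding but leaves low-grade bleeding to chance, for the first-listed risk of the drug and alongside a co-medication that the protocol says increases it. The recording text is also not the same for the two arms, and that needs repair whatever is decided about the floor.

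The size of the loss is unknown, because the documents give neither the rate of low-grade bleeding in this population nor the share of bleeds at grade 3 or above. The range of 50% to 90% lost rests entirely on the assumed 10% to 50% share. The primary analysis and the sample size are unaffected. The change should be made because it is cheap and specific, not because it would give the trial power to compare bleeding.

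**What to change.** In Section 1.2 (Research Design and Methods):

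1. Keep the grade 3 floor for general adverse events.
2. Add that bleeding of any grade is recorded in both arms from randomization to day 28, together with anticoagulant use at the time.
3. Add that any adverse event of any grade that leads to stopping study drug is recorded over the same window. This can arise only in the Aggrenox arm, so report it for that arm and do not compare it.
4. Reconcile both Recording of Adverse Events subsections and Reporting of Serious Adverse Events to one rule and one window that runs from randomization in both arms. State whether the after-withdrawal sentence is subject to the floor.
5. Add to Section 6.1 a descriptive table of bleeding by arm, by grade and by heparin use, with no hypothesis test.
6. Check the Appendix B forms for a bleeding item and add one if there is none.

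Cost: a little extra data entry. Adverse events are already reviewed at the assessments scheduled to day 28, so no visit, procedure or sample-size change follows. The downside is that low-grade bleeding in an open-label trial may be reported more readily in the Aggrenox arm; the table should say so.
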